5.1 Participant inclusion criteria

- Aged 18 years or older.
- Requiring unilateral MLLA, including patients with a pre-existing BKA who require revision to a TKA or AKA
- Able to provide consent and willing to adhere to the follow-up protocol.

5.2 Participant exclusion criteria

- Suitable for a BKA as determined by the local surgical team.
- Contraindication to either AKA or TKA as determined by the local surgical team.
- Limited life expectancy (of ≤6 months)
- Patients who require concurrent bilateral MLLA
- Evidence that the patient would be unable to adhere to trial procedures or complete questionnaires.
- Previously recruited to the HAMLET Trial

6.0 Trial processes

6.1 Participant identification

The study management team at York Trials Unit (YTU) will work closely with surgeons, clinicians and research teams at each study site to optimise the screening and recruitment process for local circumstances. Participating sites will retain screening logs to capture the number of ineligible and non-consenting patients, which will be transferred to YTU on a regular basis. For all patients who require a MLLA and are not suitable for a BKA, we will record whether the patient has been approached and/or consented to take part in the trial. If the patient has not been recruited into the trial, the reason for this will be recorded (e.g. ineligible, not approached, not consented). The trial team will use this information, alongside the qualitative investigations during the pilot phase, to identify potential areas where recruitment processes require improvement.

The screening process will be consistent for all patients undergoing a MLLA and will be performed by the treating clinician or research team in the ward or clinic when the decision to proceed to MLLA is made. Once a patient has been screened against the study eligibility criteria and deemed suitable for inclusion, they will be approached for study participation.

6.2 Informed consent

Patients will be provided with a detailed participant information sheet (PIS), which outlines the study and clearly explains the risks and benefits of trial participation. The PIS will be developed in collaboration with members of the study patient and public involvement (PPI) group.

Potential participants will receive a contact phone number so that they can ask questions of the surgeon and local research team and will be given time before deciding to participate. The patient may be asked at the time of approach whether they have had sufficient time to consider study participation, and if required to discuss the study with friends and family. They will be given further time to reach a decision if necessary.

For those who it is applicable, as part of the recruitment SWAT (refer to section 4.6.1), a recruitment video animation will also be provided.

Where participants agree to participate in the study, written consent for the study will be obtained. Specific consent will be sought to enable the sharing of identifiable data with the coordinating centre (YTU) as part of the study to facilitate the collection of outcome data. Permission will also be sought to inform the patient's GP of their study participation. All members of staff involved in eligibility sign-off and informed consent process will be required to have Good Clinical Practice (GCP) training. Depending on local circumstances, consent will be obtained in advance of, or on the day of admission for the procedure.

The responsibility for recording written informed consent will be with the site Principal Investigator (PI), or persons designated by the PI, who conducted the informed consent discussion. Designated responsibility should be recorded on the site delegation log. All consent forms will be stored in accordance with local requirements. A copy of the consent form will be given to the participant, a further copy filed in the patient medical records and the original signed copy kept in the Investigator Site File (ISF). A copy will be sent through an agreed secure method to YTU or uploaded onto the data collection database (REDCap) for central monitoring purposes.

6.3 Participant randomisation

When patients have provided written informed consent and all baseline data has been collected, an authorised and delegated member of the clinical or research team will access the randomisation area of the REDCap system managed by YTU. Randomisation will take place in the seven days prior to the date of surgery. This will ensure that the participant's treatment allocation is known to both the operating surgeon and participant beforehand. The randomisation instruments within REDCap will require the recording of information and a check of patient eligibility to avoid inappropriate entry of patients into the study. The REDCap system will then perform independent and concealed random allocation. Patients will be randomised in a 1:1 ratio, minimised by amputation aetiology (trauma vs non trauma), frailty (3 levels as per Rockwood Frailty Scale: no frailty (Score 1 to 4), mild to moderate frailty (Score 5 to 6), severe to very severe frailty (Score 7 to 8),sex, and presence or absence of pre-existing contralateral major lower limb amputation, to receive either TKA or AKA.

6.4 Blinding

The operating surgeon will be informed of the allocation and will not be blind to the intervention. Due to the nature of the intervention, blinding of participants and assessors is not possible. Data on patient preferences will be collected at baseline.

6.5 Participant follow-up

As detailed in section 4.3 participants will be followed-up within the hospital 5 days post procedure, during early assessment at a prosthetic centre (if applicable) and at 4 monthly intervals post-randomisation (4, 8, 12-, 16-, 20- and 24-months post-randomisation). The data collected both within the hospital and prosthetic centre will be done so in person by study research staff. As informed by our PPI members, remote data will be collected by study research staff via phone call with the participant. If preferred by participants, they will also have the option to provide data via digital media or postal questionnaire. Participant phone-calls will be conducted in line with the appropriate YTU Standard Operating Procedures.

Study participants should also attend any routine clinical appointments that may be scheduled outside of the study, in line with routine care pathway at the participating site.

6.6 Participant withdrawal

Participants will have the right to withdraw from the study at any time and the reason for which will be recorded in the case report form (CRF). Any participant wishing to withdraw from the study will be requested to state what personal details already collected they wish to allow the study team to retain following withdrawal. The study staff member documenting the withdrawal will request participant consent to continue to access clinical records to facilitate some level of outcome assessment in the absence of ongoing active participation in the study. If this consent is not provided, no further participant data of any kind will be collected from then onwards.

7.0 Data Management

7.1 Data entry

The data collected by sites will be entered onto REDCap, a secure online interface, specifically developed for this study. For data that are collected via participant report, only the study data in REDCap will be the source data. Data not captured on REDCap, will be stored and transferred following YTU standard operating procedures and/or University of York policies. The staff involved in the trial (both at the sites and YTU) will receive training on data protection. The staff will be monitored to ensure compliance with privacy standards.

Computerised data cleaning and validation checks will be used in addition to manual review to check for discrepancies and to ensure consistency of the data. Data will be checked according to procedures detailed in the trial specific Data Management Plan or REDCap specification document. An electronic audit trail system will be maintained within the data collection system to track all data changes in the database once the data has been saved initially into the system or electronically loaded.

7.2 Data storage

Data will be collated in REDCap with participants identified by a unique identification number (i.e. the participant identification number) only. A Trial Enrolment Log at the sites will list the participant identification numbers. YTU will maintain a list of participant identification numbers for all trial participants at each site. At the University of York, data will be held securely on the cloud-hosted REDCap server. Access to the study interface will be restricted to named authorised individuals granted user rights by a REDCap administrator at YTU. Data not within REDCap will be hosted on University of York servers. All YTU data recorded electronically will be held in a secure environment at the University of York, with permissions for access as detailed in the delegation log. Backups are taken daily and stored in a separate location. Snapshots are also taken at regular intervals throughout the day. The University's backup policy can be found here: https://www.york.ac.uk/itservices/services/backups/#tab-4

All study files will be stored in accordance with GCP guidelines. Study documents (paper and electronic) held at the YTU will be retained in a secure (kept locked when not in use) location for the duration of the trial. All essential documents, including source documents, will be retained for a minimum period of five years after study completion. The separate archival of electronic data will be performed at the end of the trial, to safeguard the data for the period(s) established by relevant regulatory requirements. All work will be conducted following the University of York's data protection policy which is publicly available (https://www.york.ac.uk/records-management/dp/).

7.3 Source data

The Investigator(s)/institution(s) will permit authorised representatives of the Sponsor and applicable regulatory agencies direct access to source data/documents to conduct trial-related monitoring, audits and regulatory inspection. Trial participants are informed of this during the informed consent discussion. Participants will consent to provide access to their medical notes.

Essential trial documentation (i.e. the documents which individually and collectively permit evaluation of the conduct of a clinical trial and the quality of the data produced) will be kept with the Trial Master File (TMF) and Investigator Site Files (ISF). The Sponsor will ensure that this documentation will be retained for a minimum of five years after the conclusion of the trial to comply with standards of Good Clinical Practice.

At YTU, the CRF data will be stored for a minimum of five years after the conclusion of the trial as paper records and in electronic format in accordance with guidelines on Good Research Practice. All paper records will be stored in a secure storage facility or off-site by York Trials Unit. All electronic records will be stored on a password protected server. The PI at any participating site will archive the trial essential documents generated at the site for the agreed archiving period in accordance with the signed Clinical Trial Site agreement or Organisational Information Document.

Once reporting and analysis are completed and published in all intended scientific journals, the anonymised data will be made available for other researchers if requested. In principle, anonymised data will be made available for meta-analysis and, where requested by other authorised researchers and journals, for publication purposes. Requests for access to data will be reviewed by the co-Chief Investigators, study Sponsor and trial team.

7.4 Source data list

Source documents are original documents, data, and records from which participants' CRF data are obtained. CRF entries will be considered source data if the CRF is the site of the original recording (e.g., there is no other written or electronic record of data). In this study source data will be captured by site staff within CRFs and also by participants during follow-up data collection.

8.1 Through Knee Amputation

TKA will be adopted as the study intervention. TKA will be defined as any technique of amputation within the vicinity of the knee joint that removes the leg below the knee joint but preserves and reattaches the patella tendon. As a pragmatic study, and in the absence of evidence to support any one technique of TKA above another, all patella tendon preserving TKA variants will be included as the perceived benefits of a longer lever and majority intact muscle insertions will be preserved. A 4-component classification system as previously described for TKA operative techniques use on the femur, patella, muscular flaps and skin incision will be used to capture the exact type of TKA performed for each participant(31).

During the recruitment period of the HAMLET study the number of TKA procedures received by patients would be expected to increase. Other aspects of the patient's care in the perioperative period will be according to local standards and as per current pathways. There are no expected excess treatment costs for the intervention arm over the control arm.

8.2 Above Knee Amputation

For the HAMLET study an AKA will be the study comparator treatment and defined as femoral division at 10-15cm above the superior margin of the patella with a standard anterior and posterior fish-mouth flap incision. As current care pathways for patients requiring MLLA often lead to patients receiving AKA, participants allocated to the comparator arm of the study will most likely receive no change in care due to study participation.

9.0 Adverse Event Management

9.1 Adverse Events

For the purposes of the HAMLET Trial, adverse events (AE) are defined as any untoward medical occurrence (i.e. any unfavourable and unintended sign, symptom or disease), experienced by a clinical trial participant and which is temporally associated with study treatment (interventions or control) and is concerned with the amputation stump, the original (index) surgery, or any event requiring medical or surgical intervention to the residual limb. Adverse events, which might be expected with this intervention are listed in Table 3.

Blood and lymphatic	Renal and urinary	Nervous system disorders	
system disorders	disorders		
Anaemia	Acute kidney injury	Dizziness	
Postoperative hemorrhage	Hematuria	Dysarthria	
Hematoma	Urinary retention	Headache	
		Paraestheis	
		Presyncope	
		Seizure/convulsions	
		Spasticity	
		Stroke	
		Transient ischemic attacks (TIAs)	
		Tremor	
		Phantom pain	
Ear and labyrinth	Immune system	Psychiatric disorders	
disorders	disorders		
Tinnitus	Allergic reaction	Agitation	
		Anxiety	
		Confusion	
		Delirium	
		Delusions	
		Hallucinations	
		Psychosis	
Cardiac disorders	Infections and	Respiratory, thoracic and	
	infestations	mediastinal disorders	
Chest pain – cardiac			
(includes angina)	Phlebitis infective	Atelectasis	
Sinus bradycardia	urinary tract	Dysponea	
Sinus tachycardia	infection (UTI)	Pleural effusion Lung infection	
Heart failure	Wound infection	(including pneumonia)	
Myocardial infarction			

Table 3: Expected Adverse events in relation to the HAMLET study

Enterocolitis	
infectious (includes	
clostridium dificile)	

9.2 Serious Adverse Events

A serious adverse event (SAE) will be defined as any untoward occurrence which is concerned with the amputation stump, the original (index) surgery, or any event requiring medical or surgical intervention to the residual limb and that:

- Results in death.
- Is a life-threatening event (that is it places the participant, in the view of the Investigator, at immediate risk of death).
- Requires unplanned hospitalisation or prolongation of existing hospitalisation (unplanned refers to emergency hospitalisations resulting in an inpatient stay; prolonged hospitalisation is deemed to be where a participant's stay is longer than expected).
- Results in persistent or significant disability or incapacity (substantial disruption of one's ability to conduct normal life functions).
- Is another important medical condition.

Important medical events that may not be immediately life-threatening, result in death or hospitalisation but may jeopardise the participant or may require intervention to prevent one of the outcomes listed in the definition of an SAE will also be considered serious.

9.3 Reporting procedures for Adverse Events and Serious Adverse Events

An appropriate member of the research team will record all directly observed AEs and all AEs reported by the trial participant following their trial treatment. In addition, sites should follow their own local procedures for the reporting of any adverse events linked to clinical care. All AEs requiring reporting will be recorded on an (S)AE form or REDCap data collection tool and will be reported to YTU within 24 hours (SAE) or 5 days (AE) of the research staff or clinical team becoming aware of the event. The severity and likely relationship to study treatments of any adverse events will be documented by the designated site clinician. An event is defined as 'related' if the event was due to the administration of any research procedure. Whereas an 'unexpected event' is defined as a type of event not listed in the protocol as an expected occurrence. All non-serious AEs, whether expected or not, should be recorded in the participant's medical notes.

At the time of reporting, the PI or delegated clinician will be asked to record an assessment of causality (to trial treatment) selecting an option from the list below:

- Definitely related- there is clear evidence to suggest a causal relationship, and other possible contributing factors can be ruled out.
- Probably related- there is evidence to suggest a causal relationship, and the influence of other factors is unlikely
- Possibly related- there is some evidence to suggest a causal relationship (e.g. the event occurred within a reasonable time after administration of the trial procedures). However, the influence of other factors may have contributed to the event (i.e. the participant's clinical condition, other concomitant events).
- Unlikely to be related- there is little evidence to suggest there is a casual relationship (e.g. the event did not occur within a reasonable time after administration of the trial procedures). There is another reasonable explanation for the event (e.g. the participant's clinical condition, or other concomitant treatments).
- Unrelated- there is no evidence of any causal relationship.

Once received, causality and expectedness will be confirmed by the CI. SAEs that are deemed to be unexpected and related to the trial will be notified to the REC and Sponsor within 15 days.

All such events will be reported to the Trial Steering Committee (TSC) and Data Monitoring Committee (DMC) at their next meetings. All participants experiencing SAEs will be followed up as per protocol until the end of the trial.

10.0 Statistical, Health Economics and Qualitative Analyses

10.1 Sample size

For the HAMLET study, a total target sample size of 386 participants, to be recruited over a period of 36 months, will be required to achieve 90% statistical power. This target was derived from a minimum clinically important difference of the EQ-5D-5L among a variety of patients with multiple co-morbidities and of similar demographics to the amputation population of 0.074 (mean) or 0.081 (median) (32). Estimating a loss to follow up rate of 20% and assuming an EQ-5D-5L difference of 0.074 with an estimated standard deviation of 0.2 (33), we would need to randomise 183 participants to each arm of the study to have 90% power (2p = 0.05); therefore, requiring a total of 386 participants.

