10.3 Statistical analysis

All analyses will be described in detail in a statistical analysis plan (SAP) which will be finalised prior to the end of data collection and will be reviewed and approved by the TSC and DMC. The SAP will be made publicly available via the ISRCTN registry. Analyses will be carried out on a locked dataset and performed using two-sided statistical tests at 5% significance under the principles of intention-to-treat. All analyses will be conducted taking into consideration the reporting requirements of the Consolidated Standards of Reporting Trials (CONSORT).

The primary analysis will compare the EQ-5D-5L scores between groups using a covariance pattern mixed-effect linear regression model, incorporating all post randomisation time points.

Treatment group, time, treatment-by-time interaction, stratification factors and baseline covariates will be included as fixed effects. Participants will be included as a random effect accounting for repeated observations per patient. Estimates of the difference in EQ-5D-5L scores will be extracted for each time point (primary outcome at 24 months) and overall, with two sided 95% CIs. Three planned subgroup analyses will be performed by including the additional baseline variable, two- and three-way interactions between the subgroup, allocation and time point in the primary analysis: frailty; amputation aetiology and sex.

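### Protocol section 10.1 gives 183 randomised per arm but a total of 386; the stated inputs give 193 per arm, so the per-arm figure needs correcting and the total does not.

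*Protocol*

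**What the plan says.** All the relevant figures are in Protocol section 10.1, apart from the allocation ratio and the test level of the analyses.

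- Section 10.1 opens with a target of 386 participants in total, which "will be required to achieve 90% statistical power".
- The assumptions are introduced with "Estimating a loss to follow up rate of 20"% and continue "assuming an EQ-5D-5L difference of 0.074 with an estimated standard deviation of 0.2".
- The per-arm requirement is "we would need to randomise 183 participants to each arm of the study to have 90% power", at a two-sided 5% level.
- The same sentence then concludes "therefore, requiring a total of 386 participants".
- Section 6.3 fixes the allocation: "Patients will be randomised in a 1:1 ratio". Section 4.1 describes a two-arm trial.
- Section 10.3 confirms the test level: analyses are "performed using two-sided statistical tests at 5% significance under the principles of intention-to-treat".

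**The concern.** The total is presented as following from the per-arm number, and it does not: twice 183 is 366. No inflation step can account for the missing 20 participants. The 20% loss is already among the assumptions that lead to 183, and 183 is described as the number to randomise, not the number to analyse. No other section reconciles the two figures.

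The same sentence attaches 90% power to 183 per arm, so a wrong per-arm figure also makes the power statement wrong as written. This is the sample-size statement for the primary outcome, in a protocol that is to be published. Anyone copying the sentence into a later document would carry forward two incompatible sizes and a power claim that cannot be reproduced. A reader of that sentence alone could not tell which size was planned.

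**Working it through.** **Inputs, all from the protocol.** Difference δ = 0.074 and SD σ = 0.2, so the standardised difference is 0.074/0.2 = 0.37. Two-sided α = 0.05 (z = 1.960), power 90% (z = 1.282), loss to follow-up 20% (all section 10.1). Allocation 1:1 (section 6.3).

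**Step 1: reproduce the total.** For two means with the normal approximation,

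n per arm = 2(z₁₋α/₂ + z₁₋β)² σ²/δ² = 2 × (1.960 + 1.282)² × 0.2²/0.074² = 153.5, rounded up to 154 evaluable per arm.

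Allowing for loss: 154/(1 − 0.20) = 192.5, rounded up to 193 randomised per arm.

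Total: 2 × 193 = 386. This is the stated total exactly.

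**Step 2: try to reproduce 183.** The nearest variants are below.

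| Variant | Per arm | Total |
|---|---|---|
| Normal approximation, divide by 0.8 | 193 | 386 |
| Two-sample t-test (154.5, so 155), divide by 0.8 | 194 | 388 |
| Multiply 154 by 1.2 instead of dividing by 0.8 | 185 | 370 |
| As printed | 183 | 386 (2 × 183 = 366) |

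Multiplying by 1.2 comes close to 183 but gives a total of 370. Using one-sided α, 80% power or the median difference of 0.081, singly or together, gives at most 162 per arm. No variant yields both 183 per arm and 386 in total.

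**Step 3: power at each per-arm figure.** With m evaluable per arm, the normal approximation is power = Φ(0.37 × √(m/2) − 1.960).

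- 183 randomised: m = 183 × 0.8 = 146.4. Then 0.37 × √73.2 − 1.960 = 1.206, and power is 88.6%. The t-test gives 88.4%. With m rounded down to 146 the values are 88.5% and 88.3%.
- 193 randomised: m = 193 × 0.8 = 154.4. Then 0.37 × √77.2 − 1.960 = 1.291, and power is 90.2%. The t-test gives 90.0%. With m rounded down to 154 the values are 90.1% and 89.9%.

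**Step 4: what would rescue 183.** Keeping 154 evaluable out of 183 needs loss of no more than 1 − 154/183 = 15.8%, against the stated 20%.

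**Step 5: size of the gap.** 386 − 366 = 20 participants, or 20/386 = 5.2% of the target. In power, it is about 1.5 percentage points.

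**The case against.** The strongest reply is that nothing operational is wrong. The recruitment target is the total, stated at the start and again at the end of section 10.1, and it is correct. The figure 183 appears once and is used nowhere else. That stands, and it sets the severity.

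A reader might infer that the per-arm figure governs when recruitment stops, so that the trial could close 20 participants short. The documents do not support this. Section 6.3 sets 1:1 minimised allocation with no cap per arm, the pilot progression criteria in section 10.2 use totals and site rates, and section 13.4 ties no committee decision to a per-arm count. Even the sentence containing 183 ends by requiring 386.

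A second reply is that the planned analysis is a repeated-measures model with baseline covariates, which is more efficient than an unadjusted comparison. If covariates correlated with the outcome at about 0.23 (assumed; 1 − r² ≈ 146.4/154.5), 183 per arm would reach 90%. This does not rescue the figure: the protocol gives no such correlation and does not size the trial on it. It would also leave 183 and 386 inconsistent.

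A third reply is that a single digit may have been misread in conversion from PDF; the progression-criteria table in section 10.2 shows such damage. The prose of section 10.1 is otherwise clean, so this is a reason to check the page and not a reason to set the point aside.

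**Conclusion.** The point holds as a low-severity correction of a stated sample-size figure. The per-arm number and the total contradict each other, and the protocol's own inputs identify the per-arm number as the error. The 90% attached to 183 per arm is overstated by about 1.5 percentage points.

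It would be wrong to conclude that the trial is underpowered. On its own assumptions it has about 90% power if it recruits the stated total.

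The power figures rest on an unadjusted comparison of two means, an SD of 0.2, a difference of 0.074 and exactly 20% loss in each arm. The contradiction between 183 and 386 rests on none of these; it needs only the 1:1 allocation. A typing error for 193 is the likely cause, but the documents do not confirm it.

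**What to change.** Check the source page first. If it reads 183, change the per-arm number in section 10.1 to 193 and add in brackets that this means 154 evaluable per arm after 20% loss. Keep the total of 386. If the sample-size paragraph has been copied into the SAP or other trial documents, make the same change there.

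The cost is one number and a short bracket. The recruitment target, the 36-month recruitment period and the analysis do not change.
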